## PROTOCOL SYNOPSIS

**Study Number and Title:** Study 0171: A Phase 3, 182-week, Open-Label Extension Study to Investigate the Safety and Tolerability Study of TD-9855 in Treating Symptomatic Neurogenic Orthostatic Hypotension (symptomatic nOH) in Subjects with Primary Autonomic Failure

**Study Short Title:** Phase 3 Open-Label Extension Study of TD-9855 for Treating symptomatic nOH in Subjects with Primary Autonomic Failure

**Estimated Number of Study Centers and Countries or Regions:** [REDACTED]

**Background and Rationale:** [REDACTED]

[REDACTED]

[REDACTED]

[REDACTED]

[REDACTED]

[REDACTED]

[REDACTED]

[REDACTED]

[REDACTED]

[REDACTED]

[REDACTED]

[REDACTED]

[figure not shown]
**Objectives:**

The primary objective of the study is to evaluate the long-term safety of TD-9855 over a 182-week period.

The exploratory objective of the study is to assess the patient reported outcome using EuroQoL Five-Dimensional Questionnaire (EQ-5D-5L).

**Study Design:**

This is a Phase 3, multi-center, open-label study to evaluate the safety and tolerability of TD-9855 in subjects with primary autonomic failures (MSA, PD, and PAF) and symptomatic nOH over 182 weeks. Given the challenges presented by the COVID-19 pandemic the trial utilizes an operational design featuring the ability to conduct protocol required visits as either in clinic or remote visits. Based upon discussion with the subject, the Investigator may conduct each study visit for a given subject either in clinic or remotely. The Investigator is recommended to conduct in clinic study visits consistent either with the standard of care for a subject outside of a clinical trial or at a minimum once per year for each subject. Tools and systems are available to sites and subjects to support remote visits (e.g., direct to subject shipping of study medication and other study supplies, standardized HIPAA/GDPR compliant telemedicine platform, in-home health nurses).

Due to the potential for resurgence of COVID-19 and its impact on both sites and subjects, these tools, mechanisms, and processes will be made available to sites and subjects who have selected the in clinic visit modality.

All sites are allowed at Investigator discretion to conduct either in clinic or remote unscheduled visit(s) for subject safety or unexpected subject medical needs outside of the regular visit schedule. Data collected during these visits may include any protocol-specified assessments which will be captured in the clinical database.

Refer to [Appendix 6](#) and the Study Reference Manual for detailed instructions for conducting subject assessments in clinic and remotely. These instructions have been provided to ensure the method and conduct of each assessment is consistent across sites and subjects for both in clinic and remote visits.

Subjects who complete Study 0170 will be eligible for this study. Following signing of the informed consent, subjects will enter Study 0171 Visit 1, which will be conducted on the same day as Visit 9 of Study 0170.

Eligible subjects will receive a single dose of [REDACTED] TD-9855 [REDACTED] ) for 182 weeks.

Subjects will complete study visits as outlined below:

[figure not shown]
- Visit 2 (Week 2)
- Visit 3 (Week 6)
- Visit 4 (Week 10)
- Visit 5 (Week 18)
- Visit 6 (Week 26)
- Visit 7 (Week 38)

- Visit 8 (Week 50)
- Visit 9 (Week 74)
- Visit 10 (Week 98)
- Visit 11 (Week 122)
- Visit 12 (Week 146)
- Visit 13 (Week 170)
- Visit 14 (Week 182)

[figure not shown]
Telephone contact will be made to assess patient safety at Weeks 14, 22, 62, 86, 110, 134, 158, and 184.

The schematic representation is as shown below:

Visits 1 to 6

Visits 7 to Telephone 8

Assessments will be conducted as outlined in the Schedule of Study Procedures ([Table 1](#)). Refer to [Appendix 6](#) and the Study Reference Manual for detailed instructions for conducting subject assessments in clinic and remotely. These instructions have been provided to ensure the method and conduct of each assessment is consistent across sites and subjects for both in clinic and remote visits.

Discontinuation of subjects may occur at any time. The stopping criteria include meeting at least one of the following rules:

- A determination from the Investigator that further administration of the investigational product may pose a safety concern to the subject.

- Sustained (at least 4 hours) SBP >180 mmHg or diastolic BP (DBP) >110 mmHg after 3 min of standing or after 5 min in the sitting position, or a sustained (at least 4 hours) SBP >180 mmHg or DBP >110 mmHg measured in the supine state (head/torso elevated at approximately 30° from horizontal position).
- Intolerable AE as determined by the Investigator.
- Subject becomes pregnant.

No dose reduction is permitted at any time.

Safety assessments for the first 26 weeks will include a physical examination, neurological examination, vital signs (HR, BP, RR and body temperature), ECGs, safety laboratory tests (hematology, chemistry, and urinalysis), C-SSRS, and AEs. Safety assessments for the remaining 158 weeks will include evaluation of adverse events and concomitant medications.

Safety will be periodically reviewed by an independent data monitoring committee, see separate charter.

Subjects will be requested to refrain from making any significant dietary changes throughout the duration of the study. Subjects must be reminded to maintain an adequate fluid intake during their scheduled visits.

**Duration of Study Participation:** Subjects will participate in this study for approximately 182 weeks of treatment and 2 weeks of follow up.

**Number of Subjects:** [REDACTED]

**Study Population:**

This study will enroll adult subjects with confirmed symptomatic nOH due to MSA, PD or PAF and who meet the inclusion and none of the exclusion criteria defined below. Eligible subjects will be subjects who complete Study 0170.

**Inclusion Criteria:**

1. Completion of Study 0170 and, in the opinion of the Investigator, would benefit from long-term treatment with TD-9855.
2. The subject must be able to understand the nature of the study and must provide written informed consent prior to the conduct of any study procedures (including any changes occurring in the subject's current therapeutic regimen).
3. The subject must be willing to continue on treatment and must continue to meet all the inclusion criteria for the preceding study (Study 0170) except, a score of  $\geq 4$  in OHS#1.

**Exclusion Criteria:**

1. Subjects may not be enrolled in another clinical trial, with the exception of purely observational studies, which are allowed.

2. Psychiatric, neurological, or behavioral disorders that may interfere with the ability of subjects to give informed consent or interfere with the conduct of the study.
3. Medical, laboratory, or surgical issues deemed by the Investigator to be clinically significant.
4. Hypersensitivity to TD-9855 or the formulation excipients.

**Test Product, Dose, and Route of Administration; Regimen; Duration of Treatment:**

[REDACTED]

**Reference Therapy, Dose, and Route of Administration; Regimen; Duration of Treatment:**

[REDACTED]

**Study Evaluations**

**Safety Assessments:**

- Physical examination
- Neurological examination
- Vital signs
- Resting ECGs
- Clinical laboratory tests including biochemistry, hematology, and urinalysis.
- Concomitant medication
- AEs
- Subject compliance to study treatment
- Incidence of falls
- Columbia Suicide Severity Rating Scale (C-SSRS)

**Statistical Methods**

[REDACTED]

[REDACTED]

**Study Endpoints:**

Primary safety and tolerability endpoints include:

- Physical examination
  - Neurological examination
  - Vital signs
  - Resting ECGs
  - Clinical laboratory tests including biochemistry, hematology, and urinalysis.
  - Concomitant medication
  - AEs
  - Subject compliance to study treatment
  - Incidence of falls
  - Columbia Suicide Severity Rating Scale (C-SSRS)
- [REDACTED]
- [REDACTED]
- [REDACTED]

**Analysis:**

The FAS (Full Analysis Set) and Safety analysis set will be identical and is defined as all enrolled subjects who have received at least one dose of TD-9855 in this study.

Descriptive summaries will be provided for demographics and baseline characteristics.

Safety data will be listed by subject and summarized using the frequency of event or descriptive statistical summaries, as appropriate. Summary tables will be provided for adverse events, hematology, biochemistry and urinalysis laboratory evaluations, vital signs, 12 lead ECG findings, and concomitant medications.

Incidence of falls will be descriptively summarized using number of falls per subject, number and percentage of subjects with at least 1 fall since the previous study visit.

[REDACTED]

### SCHEDULE OF STUDY PROCEDURES

**Table 1: Schedule of Study Procedures (Visits 1 – 6)**

Each study visit for each subject may be conducted either in clinic or remotely									
Study Week (Visit/Telephone):	Week 0 Visit 1 (0170 Visit 9)	Week 2 Visit 2 +/- 3 days	Week 6 Visit 3 +/- 3 days	Week 10 Visit 4 +/- 7 days	Week 14 Telephone 1 +/- 3 days	Week 18 Visit 5 +/- 7 days	Week 22 Telephone 2 +/- 3 days	Week 26 Visit 6 +/- 7 days	Early Termination up to Week 26
Informed Consent	X								
Inclusion / exclusion criteria	X								
Medical history, including smoking history	X								
Concomitant Medications	X a	X	X	X	X	X	X	X	X
C-SSRS	X a	X	X	X		X		X	X
[REDACTED]	[REDACTED]	[REDACTED]	[REDACTED]	[REDACTED]		[REDACTED]		[REDACTED]	[REDACTED]
Vital signs (heart rate, blood pressure, respiratory rate and body temperature)	X a, b	X b	X b	X b		X b		X b	X b
Physical examination	X a			X				X	X
Neurological examination	X a			X				X	X
12-lead electrocardiogram e	X a			X				X	X
Pregnancy Test	X a, c			X c				X c	X c
Safety Labs (chemistry, hematology, urinalysis)	X a			X				X	X
Dosing, Incidence of Falls, and Midodrine Diaries	X a	X	X	X		X		X	X
Adverse Events	X a	X	X	X	X	X	X	X	X
Dispense Study Drug	X d	X d	X d	X d		X d		X d	
Study Drug Dosing	X d								
Collect Study Drug		X	X	X		X		X	X

a. Study 0170 procedures conducted at Visit 9 will serve as the baseline assessment for Visit 1 of Study 0171.  
 b. Vital signs will be assessed after the subject has been resting for at least 5 minutes in the seated or supine position.

- c. In women of childbearing potential only, urine beta human chorionic gonadotropin ( $\beta$ hCG) test will be performed and if positive, confirmation with serum  $\beta$ hCG test is required. The pregnancy test must be confirmed negative for a subject to be eligible for this study.
- d. Study drug will be ingested in the morning at approximately the same time of day with 8 ounces of water. The exact time and day of dosing will be recorded on the mornings of study visits. Subjects must be reminded to maintain an adequate fluid intake during their scheduled visits. Subjects will start taking study drug on the day after Visit 1.
- e. ECGs are done in triplicate after the subject has been resting for at least 5 minutes in a seated or supine position before the first reading, with each replicate separated by at least 1 minute.

**Table 2: Schedule of Study Procedures (Visits 7 – 14 Extension)**

Study Week (Visit/Telephone):	Wk 38 Visit 7 +/-7 days	Wk 50 Visit 8 +/-7 days	Wk 62 Telephone 3 +/-7 days	Wk 74 Visit 9 +/-7 day	Wk 86 Telephone 4 +/-7 days	Wk 98 Visit 10 +/-7 days	Wk 110 Telephone 5 +/-7 days	Wk 122 Visit 11 +/-7 days	Wk 134 Telephone 6 +/-7 days	Wk 146 Visit 12 +/-7 days	Wk 158 Telephone 7 +/-7 days	Wk 170 Visit 13 +/-7 days	Wk 182 Visit 14 End of Treatment Early Termination after Week 26 +/-7 days	Wk 184 Telephone 8 Follow-up +/-7 days
Procedure														
Concomitant Medications	X	X	X	X	X	X	X	X	X	X	X	X	X	X
Adverse Events	X	X	X	X	X	X	X	X	X	X	X	X	X	X
Pregnancy Test a		X		X		X		X		X			X	
Dispense Study Drug	X	X		X		X		X		X		X		
Study Drug Dosing	X b													
Collect Study Drug	X	X		X		X		X		X		X	X	

a. In women of childbearing potential only, urine beta human chorionic gonadotropin (βhCG) test will be performed.

b. Study drug will be ingested in the morning at approximately the same time of day with 8 ounces of water.

## LIST OF ABBREVIATIONS AND DEFINITION OF TERMS

Abbreviation	Description
5-HT	Serotonin
ADHD	Attention-deficit hyperactivity disorder
AE	Adverse event
AESI	Adverse event of special interest
ALT	Alanine aminotransferase
AST	Aspartate aminotransferase
AUC	Area under curve
βhCG	Beta human chorionic gonadotropin
BP	Blood pressure
CFR	(United States) Code of Federal Regulations
C max	Maximum concentration recorded
CNS	Central Nervous System
eCOA	Electronic Clinical Outcome Assessment
CRF	Case report form
C-SSRS	Columbia Suicide Severity Rating Scale
DBP	Diastolic blood pressure
ECG	Electrocardiogram
EDC	Electronic data capture
ET	Early Termed
[REDACTED]	[REDACTED]
FAS	Full analysis set
FM	Fibromyalgia
GCP	Good Clinical Practice
GDPR	General Data Protection Regulation
GI	Gastrointestinal
GLP	Good Laboratory Practice
HIPAA	Health Insurance Portability and Accountability Act
HR	Heart rate
IB	Investigator's Brochure
ICF	Informed consent form
ICH	International Council for Harmonization of Technical Requirements for Registration of Pharmaceuticals for Human Use
IDMC	Independent Data Monitoring Committee
IEC	Independent Ethics Committee
IRB	Institutional Review Board
IUD	intra-uterine devices
MAD	Multiple ascending dose
MAP	Mean arterial pressure
MAR	Missing at random

Abbreviation	Description
MedDRA	Medical Dictionary for Regulatory Activities (MedDRA®)
MMRM	Mixed Model for Repeated Measures
MSA	Multiple System Atrophy
NE	Norepinephrine
NET	Norepinephrine transporter
nOH	Neurogenic Orthostatic Hypotension
NOAEL	No observed adverse event level
NRI	Norepinephrine reuptake inhibitor
OH	Orthostatic Hypotension
OHSA#1	Orthostatic Hypotension Symptom Assessment Question 1
PAF	Pure Autonomic Failure
PD	Parkinson's disease
P-gp	p-glycoprotein
PI	Principal Investigator
PK	Pharmacokinetic(s)
PP	Per-protocol
PT	Preferred term
QD	Daily
QTcF	Corrected QT interval using the Fridericia's formula
REB	Research Ethics Board
RR	Respiratory rate
RTSM	Randomization and trial supply management
SAD	Single ascending dose
SAE	Serious adverse event
SAP	Statistical analysis plan
SBP	Systolic blood pressure
SERT	Serotonin Reuptake Transporter
symptomatic nOH	Symptomatic Neurogenic Orthostatic Hypotension
SNRI	Serotonin norepinephrine reuptake inhibitor
SOC	System organ class
SOP	Standard Operating Procedure
t 1/2	Elimination half-life
TEAE	Treatment-emergent adverse event
TD-9855	Laboratory code for amprelosetine hydrochloride
US	United States
V1, V2, V3, etc.	Study Visits

## 1. INTRODUCTION

### 1.1. Background and Rationale

In healthy individuals, changes in blood pressure (BP) are highly regulated and well

[REDACTED]

[REDACTED]

[REDACTED]

[REDACTED]

[REDACTED]

[REDACTED]

[REDACTED]

[REDACTED]

[REDACTED]

## 1.2. Nonclinical Profile

A review of the nonclinical profile of TD-9855 can be found in the current version of the TD-9855 Investigator's Brochure (IB). The following is a brief summary of the pertinent findings.

### 1.2.1. [REDACTED]

[REDACTED]

SERT over DAT and various other transporter, receptor, ion channel, and enzyme targets

[REDACTED]

1.2.2. [REDACTED]

[REDACTED]

[REDACTED]

[REDACTED]

1.2.3. [REDACTED]

[REDACTED]

[REDACTED]

[REDACTED]

1.2.4. [REDACTED]

[REDACTED]

[REDACTED]

- [REDACTED]
- [REDACTED]
- [REDACTED]

[REDACTED]

**1.3.** [REDACTED]

[REDACTED]

[REDACTED]

[REDACTED]

[REDACTED]

[REDACTED]

[REDACTED]

[REDACTED]

[REDACTED]

[REDACTED]

[REDACTED]

[REDACTED]

[REDACTED]

[REDACTED]

[REDACTED]

[REDACTED]

Overall, of the 34 subjects dosed in the study, 3 subjects discontinued study drug due to

[REDACTED]

**1.3.1.** [REDACTED]

[REDACTED]

**1.4. Risks and Benefits**

Results from preclinical and clinical studies indicate that TD-9855 is [REDACTED]

[REDACTED] Efficacy of TD-9855 is being further evaluated in confirmatory studies (Studies 0169 and 0170). Study 0171 provides access to drug for subjects who participated in Study 0170 and for whom Investigators believe could benefit from longer term treatment with TD-9855.

[REDACTED]

[REDACTED]

To help ensure subject safety, subjects will be closely monitored during this study. Study visits will be conducted in the Investigator's autonomic disorders clinic or appropriately qualified research facility, or remotely using a telemedicine platform, under the supervision of qualified site personnel with help from a health care provider. The schedule of procedures requires subjects to be closely monitored on a regular basis during the dosing and follow-up periods. If any subject should incur any unexpected and untoward event during the testing procedures, the Investigator is instructed to provide the subject immediate and appropriate care as needed, including unscheduled in-clinic or remote visits.

A summary of known and potential risks to human subjects is provided in the IB in the Summary of Data and Guidance for the Investigators

## **2. OBJECTIVE**

[figure not shown]
The primary objective of the study is to evaluate the long-term safety of TD-9855 over a 182-week period.

[REDACTED]

### 3. STUDY DESIGN

#### 3.1. Overview

This is a Phase 3, multi-center, open-label study to evaluate the safety and tolerability of TD9855 in subjects with primary autonomic failures (MSA, PD, and PAF) and symptomatic nOH over 182 weeks. Given the challenges presented by the COVID-19 pandemic the trial utilizes an operational design featuring the ability to conduct protocol required visits as either in clinic or remote visits. Based upon discussion with the subject, the Investigator may conduct each study visit for a given subject either in clinic or remotely. The Investigator is recommended to conduct in clinic study visits consistent either with the standard of care for a subject outside of a clinical trial or at a minimum once per year for each subject. Tools and systems are available to sites and subjects to support remote visits (e.g., direct to subject shipping of study medication and other study supplies, standardized HIPAA/GDPR compliant telemedicine platform, in-home health nurses).

Due to the potential for resurgence of COVID-19 and its impact on both sites and subjects, these tools, mechanisms, and processes will be made available to sites and subjects who have selected the in clinic visit modality.

All sites are allowed at Investigator discretion to conduct either in clinic or remote unscheduled visit(s) for subject safety or unexpected subject medical needs outside of the regular visit schedule. Data collected during these visits may include any protocol-specified assessments which will be captured in the clinical database.

Subjects who complete Study 0170 will be eligible for this study. Following signing of the informed consent, subjects will enter Study 0171 Visit 1, which will be conducted on the same day as Visit 9 of Study 0170. Study 0170 procedures conducted at Visit 9 will serve as the baseline assessments for Visit 1 of Study 0171.

Beginning on the day after Visit 1, subjects will receive a single dose of [REDACTED] TD-9855 [REDACTED] and continue thereafter for the 182-week duration of the treatment period.

Subjects will complete study visits as outlined below:

- Visit 2 (Week 2)
- Visit 3 (Week 6)
- Visit 4 (Week 10)
- Visit 5 (Week 18)
- Visit 6 (Week 26)
- Visit 7 (Week 38)
- Visit 8 (Week 50)
- Visit 9 (Week 74)
- Visit 10 (Week 98)

[figure not shown]
- Visit 11 (Week 122)
- Visit 12 (Week 146)
- Visit 13 (Week 170)
- Visit 14 (Week 182)

Telephone contact will be made to assess patient safety on Weeks 14, 22, 62, 86, 110, 134, 158, and 184.

[figure not shown]
The study consists of 3 periods: (i) 26-week treatment, (ii) 156-week treatment extension and (iii) 2-week follow-up. The schematic representation is as shown below:

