**Figure 1: Study Schematic**

Visits 1 to 6

Visits 7 to Telephone 8

No dose reduction is permitted during the treatment periods.

Subjects unable to tolerate [REDACTED] TD-9855 will be discontinued from the study.

Assessments will be conducted as outlined in the Schedule of Study Procedures (Table 1). Refer to Appendix 6 and the Study Reference Manual for detailed instructions for conducting subject assessments in clinic and remotely. These instructions have been provided to ensure the method and conduct of each assessment is consistent across sites and subjects for both in clinic and remote visits.

At any time during the study, if a subject meets at least one of the following stopping rules, they must be discontinued and undergo an end of study visit:

- A determination from the PI (in discussion with the Sponsor’s medical monitor) that further administration of the investigational product may pose a safety concern to the subject.

- Sustained (at least 4 hours) SBP >180 mmHg or diastolic BP (DBP) >110 mmHg after 3 min of standing or after 5 mins in the sitting position, or a sustained (at least 4 hours) SBP >180 mmHg or DBP >110 mmHg measured in the supine state (head/torso elevated at approximately 30° from horizontal position).
- Intolerable AE, as determined by the PI.
- Subject becomes pregnant.

During the first 26 weeks, safety assessments will include a physical examination, neurological examination, vital signs (HR, BP, respiratory rate [RR] and body temperature), 12-lead electrocardiograms (ECGs), laboratory tests (hematology, chemistry, and urinalysis), Columbia Suicide Severity Rating Scale (C-SSRS), and monitoring of AEs. Safety assessments after Week 26 will include assessments of AEs and Concomitant Medications.

[REDACTED]

Subjects will be requested to refrain from making any significant dietary changes throughout the duration of the study. During their scheduled visits, subjects should be reminded to maintain an adequate fluid intake.

Subjects will complete the Early Termination Visit if they terminate from the study prior to Week 26. All subjects will complete the End of Treatment Visit (Visit 14) upon completion of the 182-week treatment period or if terminating early after Week 26. The Follow-up visit must be completed within 2 weeks (+/- 7 days) from the date of the last dose for all subjects who complete the 182-week treatment period or who terminate the study early at any point.

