#### 7.1.1. Adverse Events (AE)

An AE is any untoward medical occurrence in a patient or clinical trial subject administered a pharmaceutical product that does not necessarily have to have a causal relationship with this treatment. An AE can therefore be any unfavorable and unintended sign (including an abnormal laboratory finding), symptom, or disease temporally associated with the use of a medicinal product, whether or not related to the medicinal product.

- AEs may be new events.
- Pre-existing events that increase in frequency, severity or change in nature or seriousness during or as a consequence of participation in clinical studies.
- Pre- or post-treatment complications that occur as a result of a protocol-mandated procedure (such as a biopsy).
- AEs may be clinically significant changes from baseline in physical examination, laboratory tests, or other diagnostic investigation (e.g., laboratory results, x-ray findings).
- AEs may result from an overdose of the study drug.

Whenever possible, the diagnosis (rather than a series of terms related to a diagnosis) should be recorded as the AE term.

An AE does not include the following:

- Medical or surgical procedures (such as surgery, endoscopy, tooth extraction, or transfusion); the condition that leads to the procedure is an adverse event.
- Preexisting diseases or conditions present or detected before signing an informed consent form that do not worsen.
- Situations where an untoward medical occurrence has not occurred (such as hospitalization for elective surgery or social and/or convenience admissions).
- Overdose of either study drug or concomitant medication without any signs or symptoms, unless the subject is hospitalized for observation.

Any medical condition or clinically significant laboratory abnormality with an onset date prior to the date of first dose in Study 0171, is considered to be preexisting and should be documented in the medical history CRF.

Pregnancy is not an AE; however, if a female subject becomes pregnant during the conduct of the study, Theravance Biopharma, Inc. (TBPH) will be notified according to the procedures for SAE reporting as outlined in Section 7.4.3. Follow-up information regarding the outcome of the pregnancy and any fetal or neonatal sequelae will be obtained and documented.

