### **3. STUDY OBJECTIVES AND ENDPOINTS**

#### **3.1. Objectives**

##### **3.1.1. Primary Objective**

The primary objective of the study is to evaluate the long-term safety of TD-9855 over a 182-week period.

[REDACTED]

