### 8.1. Adverse Events

Adverse events are collected from signing of the informed consent form through the end of the study. Adverse events will be coded to the preferred terms of the Medical Dictionary for Regulatory Activities (MedDRA®, version 24.1).

A treatment-emergent adverse event (TEAE) will be defined as any AE that begins on or after the date of first dose of Study 0171 study drug up through 14 days after the date of last dose of study drug. AEs that begin more than 14 days after the date of last dose of study drug and AEs that begin during the period from obtaining informed consent to the start of administration of study drug will not be considered treatment-emergent and will be listed only.

The following AE summaries will be provided:

- TEAE overall summary
- TEAEs by preferred term
- TEAEs by system organ class and preferred term
- Moderate or severe TEAEs by system organ class and preferred term
- TEAEs by preferred term with frequency > 3% of safety analysis set subjects
- TEAEs by system organ class, preferred term, and severity
- Drug-related TEAEs by system organ class and preferred term
- Drug-related TEAEs by system organ class, preferred term, and severity
- Drug-related moderate or severe TEAEs by system organ class and preferred term
- Serious TEAEs by system organ class and preferred term
- Drug-related serious TEAEs by system organ class and preferred term
- TEAEs resulting in on-study deaths
- TEAEs leading to premature study drug discontinuation
- TEAEs leading to temporary interruption of study drug
- TEAEs of special interest by system organ class and preferred term (Section 8.1.1)

If no adverse events meeting a specific table definition were reported, the body of the table will contain only a statement that no events met the table definition.

The following AE listings will be provided:

- TEAEs
- AEs leading to premature study drug discontinuation
- AEs resulting in temporary interruption of study drug
- Serious adverse events
- Deaths
- Non-treatment-emergent adverse events

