### **8.1.1. Adverse Events of Special Interest**

An AE of special interest (AESI) is one of scientific and medical interest specific to understanding the investigational product and may require close monitoring and rapid communication by the investigator to the sponsor. The following are the AESIs defined for the study:

- Supine Hypertension
- Myocardial Infarction
- Cerebrovascular Accident
- Cardiac Arrhythmia
- Congestive Heart Failure
- Convulsion

The incidence of treatment-emergent AESIs will be summarized, overall (any AESI) and by system organ class and preferred term. A listing of AESIs will be provided.

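### The objective is long-term safety, but no SAP adverse event table isolates events with onset after Week 26 or relates them to the subjects still treated

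*Protocol*

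**What the plan says.** SAP 3.1.1 sets the aim: "The primary objective of the study is to evaluate the long-term safety of TD-9855 over a 182-week period". Protocol 3.1 gives the structure: "The study consists of 3 periods: (i) 26-week treatment, (ii) 156-week treatment extension and (iii) 2-week follow-up".

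The two treatment periods are observed differently. In the text after Figure 1 the protocol says: "Safety assessments after Week 26 will include assessments of AEs and Concomitant Medications". The synopsis agrees: "Safety assessments for the remaining 158 weeks will include evaluation of adverse events and concomitant medications". Tables 1 and 2 of the protocol show the same pattern, with vital signs, ECGs, laboratory tests, examinations, C-SSRS and the diaries all ending at Week 26. Protocol 7.1.1 makes test findings a source of adverse events: "AEs may be clinically significant changes from baseline in physical examination, laboratory tests, or other diagnostic investigation".

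SAP 8.1 gives treatment-emergent events a single interval: "any AE that begins on or after the date of first dose of Study 0171 study drug up through 14 days after the date of". The sentence goes on to name the end of dosing, so the interval closes 14 days after a subject stops the drug. The section then names 15 summaries, none of them by time of onset or by study period. SAP 8.1.1 does the same for events of special interest (AESIs): "The incidence of treatment-emergent AESIs will be summarized, overall (any AESI) and by system organ class and preferred term". The safety set (SAP 6.1.2) is every enrolled subject with at least one dose. Exposure (SAP 8.2) is summarized as days on drug, without person-time or number at risk by period. SAP sections 2 and 5 record that the sponsor stopped the study early with 110 enrolled, and that one analysis replaces the two that were planned.

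**The concern.** Events that begin after Week 26 are the ones that speak most directly to long-term safety. The SAP's other outputs offer little there: the analysis windows in Table 4 and the falls summary in 8.7 both end at Day 189, and the scheduled measurements have stopped. The adverse event tables are therefore the main place to look.

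Two things get in the way. First, each percentage is taken over everyone ever dosed, so subjects who left before Week 26 sit in the denominator for events they could not have had in the extension. Secondly, the intensity of observation changes at Week 26. A small number of late events could reflect less frequent contact and no scheduled testing as well as low risk. A single pooled person-time rate would not separate these, because it would mix the two regimes in the same way.

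**Working it through.** **Periods.** 26 + 156 = 182 weeks of treatment, as stated. Adding 2 weeks of follow-up gives 184, the last contact. 156 + 2 = 158, which matches the synopsis.

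**Contacts** (visit list, Tables 1 and 2, and "Telephone contact will be made to assess patient safety on Weeks 14, 22, 62, 86, 110, 134, 158, and 184").
- To Week 26: Weeks 2, 6, 10, 14, 18, 22 and 26 are 7 contacts; 26/7 = 3.7 weeks apart on average.
- Extension: Weeks 38 to 182 in steps of 12 are 13 contacts; 156/13 = 12 weeks apart.
- Ratio of spacing: 12/3.7 = about 3.2.
- Scheduled measurements after baseline: vital signs and C-SSRS at 5 visits (Weeks 2, 6, 10, 18, 26); laboratory tests, ECG and examinations at 2 (Weeks 10, 26); none later.

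**Denominator.** Let N = 110 (enrolled; the safety set may be slightly smaller). Let n be the number dosed after Week 26, which is not in the documents and is varied here by assumption. If k subjects have an event that first occurs late, the pooled table shows k/N and the at-risk incidence is k/n, so the ratio is N/n. With no late events, the upper Clopper-Pearson 95% limit (two-sided) is 1 − 0.025^(1/n). Take k = 3 as an illustration.

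| n | 110/n | 3 late cases, pooled | 3 late cases, at risk | 0 late cases, upper limit |
|---|---|---|---|---|
| 110 | 1.0 | 2.7% | 2.7% | 3.3% |
| 82 | 1.3 | 2.7% | 3.7% | 4.4% |
| 60 | 1.8 | 2.7% | 5.0% | 6.0% |
| 55 | 2.0 | 2.7% | 5.5% | 6.5% |
| 40 | 2.8 | 2.7% | 7.5% | 8.8% |
| 33 | 3.3 | 2.7% | 9.1% | 10.6% |

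**Effect on the frequency cut.** SAP 8.1 has a table of preferred terms reported by more than 3% of the safety set. 3/110 = 2.7% fails and 4/110 = 3.6% passes. A term seen only in three subjects, all late, would be left out of that table even if those three were 9.1% of the subjects at risk.

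**The case against.** The strongest reply is that the SAP does what the protocol allows. Protocol 8.5 permits safety summaries over the entire treatment period, 8.5.2 defines a single treatment-emergent interval, and no visible text promises tables by period. That stands: this is a gap in reporting, not a departure from the plan.

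A reader might infer that late events are lost or that nothing shows long-term safety. The documents do not support that. Late events count in the pooled tables and appear in the listings. AESIs, serious events and deaths have listings of their own, and the disposition listing gives first and last dose dates. In a single-arm study of 110, a patient reader could place each such event relative to Week 26.

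A reader might also infer that the pooled figures mainly describe the first 26 weeks. That cannot be shown, because person-time after Week 26 is not given. It could easily be otherwise. Suppose all 110 contributed 26 weeks and 66 went on for a mean of 40 weeks (both assumptions). At 52.18 weeks per year that is 54.8 and 50.6 person-years, so 50.6/105.4 = 48% would fall after Week 26.

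The change in ascertainment should not be overstated either. Adverse events, serious events and AESIs are asked about at every contact in both periods. Serious events and AESIs must be reported within 24 hours of awareness (7.4.3). Unscheduled assessments are allowed (6.4.3.9.4), and in-clinic visits at least yearly are recommended (3.1). Detection of deaths, infarction, stroke or convulsion depends little on scheduled tests. The loss bears more on supine hypertension, arrhythmia and laboratory or ECG findings.

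Finally, SAP 6.1.3 drops subgroup summaries because the sample is small. The worry about small numbers carries over, but the decision concerns patient subgroups, not a split by time. A small late denominator is itself something the reader needs to see.

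**Conclusion.** The point holds as a cheap improvement. None of the 15 summaries in SAP 8.1, the AESI table among them, isolates onset after Week 26 or uses the number still treated as its denominator, although the primary objective runs to 182 weeks and the observation scheme changes at Week 26.

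The size is conditional. Pooled percentages understate late incidence by 110/n only to the extent that subjects stopped before Week 26. Early termination makes some such loss likely, but the factor may be anywhere from 1.0 upwards and cannot be computed from the documents. The illustrations assume 110 in the safety set, three late cases or none, and the values of n shown. The contact counts and the end of scheduled testing at Week 26 rest on no assumption.

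**What to change.** In SAP 8.1 and 8.1.1, keep the pooled column and add two onset columns to five tables: overall TEAE summary, serious TEAEs, TEAEs leading to discontinuation of study drug, deaths, and AESIs.

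- Column (ii): subjects with at least one dose after Day 182, for events with onset after Day 182 through 14 days past the last dose.
- Column (i): the full safety set, for all other treatment-emergent events. This includes events after Day 182 in subjects whose last dose was on or before Day 182. For example, an event on Day 185 in a subject last dosed on Day 175 belongs here, since that subject is outside the denominator of column (ii).
- Show the number at risk and the person-time for each column, because late follow-up is of unequal length and crude percentages alone do not reflect that.
- Give exact 95% intervals for the serious, fatal and AESI rows.
- Footnote that scheduled testing and contact frequency differ, so the columns should not be compared directly, and that a subject with events in both periods appears in both columns but once in the pooled one.

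The cost is SAP wording and two columns in five tables, from dates already collected; study conduct is unchanged. The downside is that column (ii) may have small numbers and wide intervals.
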